8.3 Endpoint Definitions

Primary Endpoint:

- The proportion of subjects who achieve: 1) HBV DNA < 50 IU/mL (approximately 300 copies/mL) using the Roche COBAS[®] TaqMan HBV Test for use with the High Pure System (HPS) assay; **and** 2) HBeAg seroconversion (undetectable HBeAg AND detectable anti-HBe antibodies) at Week 48 of study treatment.

Key Secondary Endpoints:

- Proportion of subjects with HBV DNA < 50 IU/mL using the Roche COBAS[®] TaqMan HBV Test for use with the High Pure System (HPS) assay at Week 48;
- Proportion of subjects with HBV DNA < LOQ (29 IU/mL) using the Roche COBAS[®] TaqMan HBV Test for use with the High Pure System (HPS) assay at Week 48;
- Proportion of subjects with serum ALT $\leq 1 \times$ ULN at Week 48;
- Proportion of subjects with HBe seroconversion (undetectable HBeAg and presence of anti-HBe antibodies) at Week 48;
- Proportion of subjects who achieved sustained HBeAg seroconversion during off-treatment follow-up among subjects who achieved HBe seroconversion (undetectable HBeAg and presence of anti-HBe antibodies) at end of treatment.

Other Secondary Endpoints:

- The number and percent of subjects with adverse events (including palatability issues), serious adverse events, discontinuations due to adverse events, and HBV disease progression through Week 48;
- Proportion of subjects who maintained HBeAg seroconversion at Week 96 (end of blinded therapy) among subjects who achieved HBeAg seroconversion at Week 48;
- Histological analysis among subjects with available liver biopsy.

Exploratory Endpoints:

- Proportion of subjects who achieve HBV DNA < 50 IU/mL using the Roche COBAS[®] TaqMan HBV Test for use with the High Pure System (HPS) assay and serum ALT $\leq 1 \times$ ULN at Week 48 of treatment;
- Proportion of subjects who achieve HBV DNA < LLD (10 IU/mL) using the Roche COBAS[®] TaqMan HBV Test for use with the High Pure System (HPS) assay at Week 48;
- Proportion of subjects with HBsAg loss at Weeks 48 and 96 on study treatment;
- Proportion of subjects with HBV DNA < 50 IU/mL using the Roche COBAS[®] TaqMan HBV Test for use with the High Pure System (HPS) assay at Week 96 on study treatment;
- Proportion of subjects with ALT $\leq 1 \times$ ULN at Week 96 on study treatment;
- Proportion of subjects with HBeAg loss at Weeks 48 and 96 on study treatment;

- Proportion of subjects with HBe seroconversion at Week 96 on study treatment;

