8.4 Analyses

Binary variables will be summarized by counts and percentages. Comparisons of binary variables will be based on Cochran-Mantel-Haenszel (CMH) statistic stratified by age group. Confidence intervals (CI) for differences in proportions will be based on the normal approximation to the binomial distribution with unpooled proportions used in the computation of the standard error of the difference. The CI procedure will be used for both primary and secondary efficacy endpoints if applicable.

Continuous variables will be summarized with univariate statistics (eg, mean, median, standard deviation, minimum, and maximum).

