8.4.3 Efficacy Analyses

The primary and key secondary analyses will be based on randomized and treated subjects (modified intention-to-treat [ITT]). For the analysis of the primary and the key secondary endpoints at Week 48, subjects who discontinue from study prior to Week 48 or have missing measurement at Week 48 will be considered as failures at Week 48 (Non-completer = Failure). Sensitivity analyses will be performed in order to account for possible effects of early discontinuation, in which subjects who discontinue from study prior to Week 48 or have missing Week 48 measurements are excluded (Non completer = Missing). Treatment comparison for the primary endpoint and key secondary endpoints will be performed stratified by age group using Cochran-Mantel-Haenszel (CMH) weights. The difference in proportions (ETV - placebo), p-value, and 95% Confidence Interval (CI) will be presented. ETV will be considered superior to placebo if the p-value is < 0.05 . The CI for the differences in proportions will be based on the normal approximation to the binomial distribution. A two-stage testing procedure will be employed for testing the primary and key secondary endpoints. In the first stage, the test for primary endpoint will be performed. Provided test result of the primary endpoint is significant (the p-value < 0.05), the second stage tests of

the key secondary endpoints will be conducted. Because the test for the key secondary endpoint will be conducted only if the test for the primary endpoint is successful, significance levels will not be adjusted for the first stage testing. All tests for treatment comparison will be two-sided at a significance level of 0.05. In addition, treatment comparisons for the primary endpoint and key secondary endpoints will be performed within each age group. Subgroup analysis by age group will be exploratory.

For exploratory efficacy endpoints, subjects who discontinue from study prior to the analysis week or have missing analysis week measurements will be excluded (Non completer = Missing). The difference in proportions along with its 95% CI will be presented.

Genotypic resistance to ETV will be described.

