## 4.2 Key Secondary Endpoints

- Proportion of subjects with HBV DNA < 50 IU/mL using the Roche COBAS® TaqMan HBV Test for use with the High Pure System (HPS) assay at Week 48;
- Proportion of subjects with serum ALT  $\leq 1 \times$  ULN at Week 48;
- Proportion of subjects with HBV DNA < limit of quantification (LOQ; 29 IU/mL) using the Roche COBAS® TaqMan HBV Test for use with the High Pure System (HPS) assay at Week 48;
- Proportion of subjects with HBeAg seroconversion (undetectable HBeAg and presence of anti-HBe antibodies) at Week 48;
- Proportion of subjects who achieved sustained HBeAg seroconversion during off-treatment follow-up among subjects who achieved HBe seroconversion (undetectable HBeAg and presence of anti-HBe antibodies) at end of treatment.

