- **Year 2 Efficacy Cohort** is treated subjects grouped as-randomized and according to observed Week 48 seroconversion status: ETV, PBO, ETV S48, PBO S48, ETV NS48 and PBO NS48 (S = seroconverter; NS = non-seroconverter). All treated subjects are included in ETV and PBO.
  - **Year 2 Primary Efficacy Cohort** is treated subjects in both Primary and Year 2 Efficacy Cohorts.
- **Year 3 Efficacy Cohort** is observed Week 48 non-seroconverters grouped as-randomized according to observed Week 96 seroconversion status: ETV S96, ETV NS96, PBO S96 and PBO NS96.
- **Year 4 Efficacy Cohort** is PBO-randomized observed non-seroconverters at both Weeks 48 and 96 who seroconverted at Week 144.
- **All ETV Efficacy Cohort** is treated as-randomized ETV subjects and PBO-randomized subjects who received open-label ETV.
- **Post-Year 1 Efficacy Cohort** is treated subjects grouped as-randomized: ETV, PBO, PBO subjects who only received blinded PBO (PBO BL), PBO subjects who received open-label ETV (PBO OL), and All ETV (ETV and PBO OL combined; see previous bullet).
- **Year 2 Safety Cohort** is treated subjects grouped as-treated: ETV, PBO subjects who only received blinded PBO (PBO BL), and PBO subjects who received open-label ETV (PBO OL). In addition, subjects must have received open-label ETV or > 54 weeks of study therapy (the upper bound of the Week 48 visit window; see [Sections 7.4.1](#) and [8.4](#)).
- **All ETV Safety Cohort** is as-treated ETV subjects and as-treated PBO subjects who received open-label ETV.
- **Post-Year 1 Safety Cohort** is treated subjects grouped as-treated: ETV, PBO, PBO subjects who only received blinded PBO (PBO BL), PBO subjects who received open-label ETV (PBO OL), and All ETV (ETV and PBO OL combined; see previous bullet).

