### **7.5 Efficacy**

Efficacy endpoints are presented by as-randomized treatment regimen for treated subjects.

Binary efficacy endpoints are analyzed using 2 algorithms:

- Non-Completer = Failure (NC = F): The numerator is based on subjects meeting the response criteria. The denominator is based on treated subjects. Subjects who have missing data at the analysis week are considered as failures.
- Non-Completer = Missing (NC = M): The numerator is based on subjects meeting the response criteria. The denominator is based on subjects with data at the analysis week. Subjects who have missing data at the analysis week are excluded.

Treatment regimens are compared using a difference in proportions (ETV - PBO), 95% confidence interval (CI) and p-value based on  $NC = F$  for the primary endpoint and key secondary endpoints. Analyses are stratified by age randomization strata (see [Section 7.3.4](#)). The proportions are computed within each stratum, and combined using a weighted average with weights proportional to stratum size (Cochran-Mantel-Haenszel [CMH] weighting). ETV will be considered superior to PBO if the p-value is  $< 0.05$ . CIs for differences in proportions are based on the stratified normal approximation to the binomial distribution with unpooled proportions used in the computation of the standard error of the difference.

A two-stage testing procedure will be employed for testing the primary and key secondary endpoints using  $NC = F$ . In the first stage, the test for primary endpoint will be performed. Provided the test result of the primary endpoint is significant (p-value  $< 0.05$ ), the second stage tests of the key secondary endpoints will be conducted. Because the tests for the key secondary endpoints will be conducted sequentially only if the test for the primary endpoint is successful, significance levels will not be adjusted for the first stage testing. All tests for treatment comparison will be two-sided at a significance level of 0.05.

For binary composite endpoints involving several components (eg, primary efficacy endpoint), only subjects who meet the response criteria for all components are considered to be responders for the composite endpoint. In addition, subjects who meet the response criteria for some components but are missing other components are considered to be missing the composite endpoint.

See also [Sections 8.4 to 8.8](#) for additional conventions.

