### **7.5.2 Key Secondary Endpoints**

The tests of the key secondary endpoints are conducted sequentially in the order specified below, provided the test result of the primary endpoint is significant. The  $n$ th key secondary endpoint is tested provided the test result of the  $(n-1)$ st key secondary endpoint is significant ( $n = 1, 2, \dots, 5$ ).

Treatment regimens are compared (ETV - PBO) with a difference in proportions and p-value at Week 48 on treatment for the Primary Cohort at the primary analysis (see [Sections 6.3](#) and [9](#)) using  $NC = F$ , unless specified otherwise.

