#### **7.5.2.5 Sustained HBeAg Seroconversion During Off-Treatment Follow-up**

Response rates of HBeAg seroconversion are presented by treatment regimen at EOD (end of dosing) and each scheduled visit during off-treatment follow-up through Week 192 using  $NC = F$

and NC = M for the Year 2 Efficacy Cohort with HBeAg seroconversion at EOD. Rates using NC = F are shown only through off-treatment follow-up Week 48.

Treatment regimens are compared between treated subjects with HBeAg seroconversion at both on-treatment Week 48 and EOD (ETV S48 - PBO S48; NC = F) with a difference in proportions and p-value at off-treatment follow-up Week 24 at the final analysis, provided the test result of HBeAg seroconversion was significant at the primary analysis (see [Section 9](#)).

Sustained HBeAg seroconversion is summarized analogously with response rates using NC = M for the Post-Year 1 Efficacy Cohort with HBeAg seroconversion at EOD.

Sustained HBeAg seroconversion at off-treatment follow-up Week 24 is also summarized by subgroups for treated subjects with HBeAg seroconversion at EOD (see [Section 7.5.1](#)).

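### The fifth key secondary test compares durability between groups selected on post-randomisation seroconversion, so its p-value is not a randomised comparison, and it rests on a handful of placebo subjects

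*SAP*

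**What the plan says.** SAP 7.5.2 fixes the order of the five key secondary endpoints: "The tests of the key secondary endpoints are conducted sequentially in the order specified below". Each is tested only if the one before it was significant. SAP 7.5.2.5 specifies the fifth: "Treatment regimens are compared between treated subjects with HBeAg seroconversion at both on-treatment Week 48 and EOD". The contrast is ETV S48 minus PBO S48, counting non-completers as failures, with a difference and a p-value at off-treatment Week 24. It is run at the final analysis, on condition that HBeAg seroconversion (step 4, SAP 7.5.2.4) was significant at the primary analysis.

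SAP 7.5 gives one decision rule for the primary and key secondary comparisons: "ETV will be considered superior to PBO if the p-value is" below 0.05.

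Protocol 8.3 defines the endpoint as "Proportion of subjects who achieved sustained HBeAg seroconversion during off-treatment follow-up among subjects who achieved HBe seroconversion", and SAP 4.2 takes the denominator "among subjects who achieved HBe seroconversion (undetectable HBeAg and presence of anti-HBe antibodies) at end of treatment". Neither definition contains the Week 48 condition that SAP 7.5.2.5 adds.

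On the statistic, Protocol 8.4 says "Comparisons of binary variables will be based on Cochran-Mantel-Haenszel (CMH) statistic stratified by age group", and Protocol 8.4.3 says "Treatment comparison for the primary endpoint and key secondary endpoints will be performed stratified by age group using Cochran-Mantel-Haenszel (CMH) weights". SAP 7.5 describes stratum weights, and an unpooled standard error for the confidence interval, but does not name the statistic behind the p-value. Neither document gives an expected count or power for the fifth test, or warns that it does not compare randomised groups.

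**The concern.** Being seroconverted at Week 48 and at end of dosing (EOD) is an outcome, so the two groups are formed after randomisation. The test is reached only after step 4 has given evidence that treatment changes who enters the subset. Children who seroconvert on ETV may include many who would not have done so on placebo, and they may keep seroconversion more or less often than the rest. Controlling alpha across the sequence does not remove that selection.

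A p-value below 0.05 would fall under the superiority rule and could be reported as ETV being superior on durability, although part or all of the difference could come from who seroconverted. A p-value above 0.05 would say little, because the placebo group is so small.

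There is a smaller complication. Under Protocol 4.1.1, a placebo child who seroconverts by Week 48 and reverts before Week 96 moves to open-label ETV. If seroconverted again at EOD, that child still counts as PBO S48. The documents give no rate for this.

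**Working it through.** **The plan's own figure.** The only stated power is for the primary endpoint: 20% vs 1%, 2:1, two-sided 0.05, 123 subjects, 90% (SAP 5). The usual pooled formula, with average rate (0.01 + 2 × 0.20)/3 = 0.1367, gives placebo n = [1.96 × √(1.5 × 0.1367 × 0.8633) + 1.2816 × √(0.0099 + 0.16/2)]² / 0.19² = (0.825 + 0.384)² / 0.0361 ≈ 40.5. That is 41 placebo and 123 in total, with 90.4% power. The figure reproduces, but it does not bear on the fifth test.

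**Inputs for the fifth test**
- Arms: 120 and 60 (Protocol synopsis). The Primary Cohort is 82 and 41 (SAP 5).
- ETV seroconversion: at least 20%. The 20% is for seroconversion plus HBV DNA suppression, so it is a floor for seroconversion alone. The documents give no rate for seroconversion alone; 30% is assumed as an upper case.
- Placebo seroconversion: 3/57 = 5.3%, or 10% (both SAP 5).
- Population: all treated subjects. SAP 7.5.2 defaults to the Primary Cohort unless stated otherwise; SAP 7.5.2.5 refers to treated subjects, the Year 2 Efficacy Cohort and the final analysis.

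**Expected Week 48 seroconverters**
- ETV: 120 × 0.20 = 24 or more.
- Placebo: 60 × 0.053 = 3.2, to 60 × 0.10 = 6.

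**After step 4 succeeds.** Stratified CMH was simulated in the 82/41 cohort (300,000 runs), keeping runs with z > 1.96 and then adding the other 38 ETV and 19 placebo subjects. Only step 4 was modelled.

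| ETV rate | Placebo rate | Step 4 passes | Mean placebo seroconverters at Week 48 |
|---|---|---|---|
| 20% | 5.3% | 61.5% | 2.5 |
| 20% | 10% | 26.9% | 4.2 |
| 30% (assumed) | 5.3% | 94.5% | 3.0 |
| 30% (assumed) | 10% | 73.8% | 5.3 |

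Exact enumeration with an unstratified pooled test gives the same means to one decimal place. The chance of two or fewer placebo subjects is 54% or 17% at ETV 20%, and 40% or 7% at ETV 30%.

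**EOD condition.** It can only lower these counts. Without the step 4 condition, an assumed 70 to 90% retention from Week 48 to EOD gives ETV 24 × 0.7 = 16.8 to 24 × 0.9 = 21.6, and placebo 3.2 × 0.7 = 2.2 to 6 × 0.9 = 5.4.

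**Selection (illustration only).** Assume that every child who seroconverts on placebo would also do so on ETV. Assume too that children who seroconvert only on ETV stay seroconverted 90% of the time and the others 70%, whatever the arm.
- Share of ETV seroconverters who need ETV: (0.20 − 0.053)/0.20 = 0.735, or (0.20 − 0.10)/0.20 = 0.50.
- ETV durability: 0.265 × 0.7 + 0.735 × 0.9 = 0.847, or 0.5 × 0.7 + 0.5 × 0.9 = 0.80. Placebo: 0.70.

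That is a 10 to 15 point difference with no effect of treatment on any child's durability. Swapping the two rates gives 10 to 15 points against ETV.

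**Operating characteristics of stratified CMH** (200,000 runs, subjects spread evenly over the three age strata, non-computable tables counted as no rejection)
- Equal durability of 70, 80 or 90%, 24 vs 3, 4 or 6: rejection 3.6 to 5.2%.
- Power for 90% vs 70% (assumed): 24 vs 3, 21.5%; 24 vs 4, 23.3%; 24 vs 6, 26.1%; 25 vs 2, 19.0%; 25 vs 3, 21.8%; 27 vs 4, 24.2%.

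**Precision.** Exact 95% intervals for placebo durability: 3/3, 29 to 100%; 5/6, 36 to 99.6%; 6/6, 54 to 100%.

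**The case against.** The best defence is that this is the last step, that nothing depends on it, and that conditioning on responders is built into the protocol's own endpoint. Protocol 2.2 asks only for durability to be assessed, and neither document says in words that it will make a randomised durability claim. All of that is true and limits the seriousness. It does not remove the problem: the p-value stands in the confirmatory sequence under a superiority rule, without a caveat.

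Some stronger readings are tempting but not supported.
- **Inflated type I error.** If the p-value used the unpooled standard error, equal durability would be rejected 16 to 42% of the time. The documents assign that standard error to confidence intervals, and Protocol 8.4 names CMH for comparisons. With CMH the error is about nominal.
- **A known bias towards ETV.** The 10 to 15 points rest on assumed durability rates and on ETV at exactly 20%. They show that selection can matter, not how much or in which direction.
- **24 and 3 to 6 as the tested counts.** They are Week 48 counts, before the EOD condition.
- **The added Week 48 condition as a defect.** SAP 7.5.2.5 states it openly. For a between-arm display it is useful, because EOD alone would admit placebo children who seroconverted on open-label ETV.

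Much of the descriptive reporting is already planned. SAP 7.5.2.5 gives rates by regimen, and SAP 6.3 already separates "PBO subjects who only received blinded PBO (PBO BL), PBO subjects who received open-label ETV (PBO OL), and All ETV".

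**Conclusion.** The concern stands on interpretation and information, not on false-positive control under equal durability. The fifth p-value compares groups selected on an outcome that step 4 must first find to differ by arm, so it cannot support a randomised claim about durability, whichever way it falls.

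The expected placebo group is about 2.5 to 5.3 Week 48 seroconverters after step 4, for ETV seroconversion of 20 to 30%, and fewer after the EOD condition. Power is about 19 to 26% for 90% vs 70% at 24 to 27 ETV and 2 to 6 placebo subjects. This rests on including all 180 subjects, on placebo rates of 5.3 to 10%, and on the assumed 30% ETV and 90%/70% durability rates. If only the Primary Cohort were meant, Week 48 counts would be smaller: 82 × 0.20 = 16.4 ETV, and 41 × 0.053 = 2.2 to 41 × 0.10 = 4.1 placebo.

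The primary and first four key secondary tests are unaffected. The point is worth correcting because the correction is cheap.

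**What to change.** - End the alpha-controlled sequence at SAP 7.5.2.4 and adjust the count of five in SAP 7.5.2.
- In SAP 7.5.2.5, delete the p-value for ETV S48 minus PBO S48 and state that the superiority rule in SAP 7.5 does not apply to this endpoint.
- Keep the planned by-arm sustained rates for subjects seroconverted at Week 48 and EOD, add exact 95% confidence intervals, and label them descriptive.
- Show separately any placebo-arm child who received open-label ETV before EOD, using the PBO BL and PBO OL labels already in SAP 6.3.

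This needs no new data and still meets the Protocol 2.2 objective. The cost is that durability carries no confirmatory p-value. Because Protocol 8.3 lists it as a key secondary endpoint and Protocol 8.4.3 has those endpoints tested, a protocol amendment may be needed.

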### **7.5.3 Other Year 1 Efficacy**

#### **7.5.3.1 Response Rates**

The following binary endpoints are summarized by treatment regimen with response rates using NC = F and NC = M at baseline and each scheduled visit on treatment through Week 48:

- HBV DNA < 50 IU/mL and ALT normalization
- HBV DNA < LLD
- HBV DNA < LOQ, LOQ - < 50, 50 - < 172, 172 - < 1,720, 1,720 - < 17,200 and  $\geq 17,200$  IU/mL
- HBeAg loss (HBeAg negative)
- HBsAg loss (HBsAg negative)
- HBsAg seroconversion (HBsAg negative and HBsAb positive).

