### 5 SAMPLE SIZE AND POWER

One hundred and twenty-three (123) subjects (randomized 2:1 to ETV vs placebo) in this study provide 90% power to show superiority of ETV versus PBO assuming a response rate for the primary endpoint HBV DNA by PCR < 50 IU/mL (approximately 300 copies/mL) and HBeAg seroconversion of 20% for ETV and 1% for PBO. A two-sided significance level of 0.05 is used. Subjects who either discontinue from study treatment prior to Week 48 or have having missing Week 48 HBV DNA or HBeAg serology measurement are considered as failures at Week 48 (Non-Completer = Failure). The efficacy estimate for ETV is derived from an analysis of the identical endpoint (HBV DNA by PCR < 300 copies/mL and HBeAg seroconversion) in the pivotal Phase 3 study of HBeAg-positive subjects, (AI463022). The efficacy estimate for PBO is derived from evidence in the literature which shows that whereas spontaneous seroconversion occurs at a relatively high rate in children, viral replication remains detectable using sensitive PCR assays. The results of the Gilead Sciences' pediatric CHB study (GS 518) support this estimate; 3 of 57 placebo treated subjects (5.3%) achieved HBeAg seroconversion, but only 1 of 58 subjects (1.7%) achieved HBV DNA < 2.23 log10 copies/mL at Week 48.

This sample size also fulfills the requirement that the ETV integrated pediatric safety database has at least 100 pediatric subjects who have received ETV for at least 48 weeks; this database will be comprised of subjects currently enrolled in study AI463-028 and from this study (AI463-189).

Currently 24 nucleoside naive subjects are enrolled in AI463-028; all 24 would have had 48 weeks of safety data collection by the time study AI463-189 reaches Week 48.

Based on the original planning for study AI463-189, it is estimated that 175 subjects will be enrolled to have approximately 123 subjects randomized (approximately 30% screen failure rate). Randomization is 2:1 (ETV 82: PBO 41); assuming a 10% drop out rate per year and even enrollment for 2 calendar years, approximately 72 ETV randomized subjects will have 48 weeks of safety data by study Week 144. This brings the number of subjects that will be included in the integrated safety database at the end of study Week 144 to approximately 96 subjects.

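### Applying NC = F to the HBV DNA bands makes the top-band share the lowest value compatible with the data, and the bands do not sum to 100%

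*SAP*

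**What the plan says.** SAP 7.5 defines the two algorithms for binary efficacy endpoints. For NC = F, "The numerator is based on subjects meeting the response criteria". Every treated child counts in the denominator, and a missing value is settled by the rule "Subjects who have missing data at the analysis week are considered as failures". For NC = M the numerator is the same, but "Subjects who have missing data at the analysis week are excluded".

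SAP 7.5.3.1 asks for its list to be "summarized by treatment regimen with response rates using NC = F and NC = M at baseline and each scheduled visit on treatment through Week 48". One item on that list is the HBV DNA distribution in six bands: below LOQ, then "LOQ - < 50, 50 - < 172, 172 - < 1,720, 1,720 - < 17,200", then 17,200 IU/mL and above. SAP 7.5.4 repeats the bands, again under both algorithms, through Week 96. Neither section makes an exception for bands that describe a poor outcome, and neither specifies a row for missing values. SAP 8.6 says only how results below LOQ or LLD are identified and which value they take in continuous analyses.

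Elsewhere the same bands are handled differently. SAP 7.5.7 (on ETV treatment) and 7.5.8 (off-treatment follow-up) use NC = M only. For exploratory efficacy endpoints, Protocol 8.4.3 says that subjects who discontinue before the analysis week or "have missing analysis week measurements will be excluded (Non completer = Missing").

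**The concern.** Calling a missing child a failure is cautious for HBV DNA below 50 IU/mL, because failure there is the bad result. For the band at 17,200 IU/mL and above, failure means not being in the worst band, so the same rule lowers the reported share of highly viremic children. For the middle bands, failure has no clear meaning at all.

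The starting point makes this easy to misread. Inclusion criterion 2d in Protocol 4.2.1 requires at least 10^5 copies/mL at screening, which Protocol Table 6.9.1 gives as 17,200 IU/mL. Essentially every eligible child therefore enters in the top band. If some children later have no value, the NC = F share in that band falls even when no child's viral load has changed. A reader of that column alone could take drop-out for viral decline.

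**Working it through.** The plan states no figure for the band table, so there is none to reproduce. The check applies the written definitions.

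**Inputs from the documents**
- NC = F and NC = M definitions: SAP 7.5.
- Drop-out: SAP 5 plans on "assuming a 10% drop out rate per year and even enrollment for 2 calendar years". The yearly 10% is used as the missing fraction at Week 48.
- Arm sizes in the Primary Cohort: 82 ETV and 41 placebo (SAP 5).
- Conversion: 5.82 copies = 1 IU (Protocol 6.9.1). 100,000/5.82 = 17,182, which the table rounds to 17,200.

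**Assumption.** The observed share in the top band is not in the documents. It is varied from 30% to 95%.

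**Formulas.** Let N be the number treated, m the missing fraction and x the number observed in a band. The number with data is N(1 - m), and p = x / [N(1 - m)].
- NC = M: p.
- NC = F: x/N = p(1 - m).
- Upper bound, with every missing child in the band: p(1 - m) + m.
- Sum of the six NC = F rows: (1 - m) × 1 = 1 - m.

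The true share lies between p(1 - m) and p(1 - m) + m, so NC = F reports the lower end. It is exact only if no missing child is at or above 17,200 IU/mL.

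**Top band**

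| m | NC = M (p) | NC = F | All missing in top band | Sum of NC = F rows |
|---|---|---|---|---|
| 5% | 30% | 28.5% | 33.5% | 95% |
| 5% | 95% | 90.3% | 95.3% | 95% |
| 10% | 30% | 27.0% | 37.0% | 90% |
| 10% | 60% | 54.0% | 64.0% | 90% |
| 10% | 95% | 85.5% | 95.5% | 90% |
| 20% | 30% | 24.0% | 44.0% | 80% |
| 20% | 95% | 76.0% | 96.0% | 80% |

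**No virological change.** An arm wholly in the top band (p = 100%) with 10% missing shows 100% × 0.9 = 90% under NC = F.

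**Effect on the apparent difference between arms**, with assumed shares of about 95% (placebo) and 30% (ETV):
- 4 placebo and 8 ETV children missing. Placebo: 35/37 = 94.6% (NC = M) and 35/41 = 85.4% (NC = F). ETV: 22/74 = 29.7% and 22/82 = 26.8%. The ETV - placebo gap goes from -64.9 to -58.5 points.
- 10 placebo and 2 ETV children missing. Placebo: 29/31 = 93.5% and 29/41 = 70.7%. ETV: 24/80 = 30.0% and 24/82 = 29.3%. The gap goes from -63.5 to -41.5 points.

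In general, moving from NC = M to NC = F changes the gap by p(placebo) × m(placebo) - p(ETV) × m(ETV). At 95% and 30% it widens in favour of ETV only if the ETV missing fraction exceeds 95/30, or about 3.2 times, the placebo one.

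**The case against.** The strongest reply is that little is lost. The sentence that calls for NC = F also calls for NC = M, so the observed-case distribution is already planned and the missing count can be worked out from the denominators. A worst-case figure is also available: 100% minus the NC = F rate below 50 IU/mL (SAP 7.5.2.1) counts every missing child as at or above 50. Only the split of missing children among the higher bands is absent. The bands also have no planned difference, confidence interval or p-value. All of this stands, and it limits the point to presentation.

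Two further replies stand in part. SAP 7.5.7 and 7.5.8 use NC = M for every endpoint they list, so they show a workable format rather than a choice made for the bands. SAP 7.1 leaves table formats to a Data Presentation Plan that is not among the documents and may already contain a missing row. The SAP text nevertheless gives a rule, and that rule works in the wrong direction for these bands.

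Some stronger readings are tempting but not supported:
- A reader might infer that the rule flatters ETV, particularly through placebo children who start rescue and so lack an on-treatment Week 48 value. Extra placebo missingness shrinks the apparent ETV advantage, as shown above.
- A reader might apply two-year drop-out (1 - 0.9^2 = 19%) to both arms at Week 96. SAP 7.5.4 summarizes the overall placebo group only through Week 48, and its seroconverter and non-seroconverter groups require an observed Week 48 status. At most, 19% fits the overall ETV column.
- A reader might say that missing children are classified as having low viral load. They are placed in no band.
- A reader might see a breach of Protocol 8.4.3. The bands are not in the exploratory list of Protocol 8.3, so that rule is supporting evidence only.

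**Conclusion.** The point holds as a minor flaw in a descriptive table. As SAP 7.5, 7.5.3.1 and 7.5.4 are written, the NC = F share at 17,200 IU/mL and above is below the NC = M share by a relative amount equal to the missing fraction. At 10% missing that means 27.0% instead of 30%, or 85.5% instead of 95%, and rows that total 90%. The 10% is the plan's yearly drop-out; the observed shares are assumptions. The shortfall is measured against NC = M. Against the unknown true share, one can say only that NC = F is at or below it.

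Inference is untouched. The primary endpoint and the key secondary endpoints are favourable outcomes, for which NC = F works as intended, and the sample size does not depend on this table.

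**What to change.** In SAP 7.5.3.1 and 7.5.4, take the HBV DNA bands out of the NC = F list, summarize them with NC = M only, as in 7.5.7 and 7.5.8, and report the number missing at each visit. If the all-treated denominator is wanted, keep it but add a missing row so that the column totals 100%. Keep NC = F for the favourable thresholds: below 50 IU/mL, below LOQ and below LLD.

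The cost is one sentence in each section and a change to the table shell. No data collection, sample size or test is affected. If the Data Presentation Plan already has a missing row, a cross-reference to it is enough.
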